- 13. For female patients (local urine pregnancy test in women of child bearing potential)
- 14. Fasting blood samples for central lab testing except for urine dipstick, which is to be done locally; upon positive result at site for leukocyte esterase (for white blood cells [WBC]) or nitrites, a midstream urine sample for urine culture (for central lab analysis) should be taken.
- 15. Self Monitoring Blood Glucose (SMBG) device to be provided at Visit 2 for one OAD, Visit 4 for liraglutide plus one OAD, and Visit 6 for liraglutide alone. Instruction on how the device should be used and the frequency of the measurements should be done when SMBG is provided. Additional instructions and training may be done on other visits as per investigator's discretion and considering patient compliance with protocol-defined measurement and clinical status of the patient.
- 16. Throughout the whole trial participation, SMBG testing is recommended to be done daily prior to breakfast but should be performed at least weekly prior to breakfast and at any time when the patient is symptomatic, i.e., experiences signs/symptoms of hyper- or hypoglycaemia.
- 17. At all the visits, the respective medication number has to be allocated to the patient via IRT.
- 18. For the screening Visit 1, laboratory only includes liver transaminases (AST and ALT), alkaline phosphatase (ALP), serum creatinine, TSH and urinalysis in addition to HbA1c and FPG.
- 19. HbA1c at Visit 6 is to be skipped if patients are on liraglutide alone.
- 20. In case of early discontinuation from double-blind treatment, Visit 15/EOT visit has to be performed within 7 days of the last dose of the study drugs.

- 21. For patients who completed the trial without any persisting adverse event at Visit 15/EOT, a Visit 16 (Follow-up visit) can be performed as a phone visit (only information on SMBG log, adverse events, and concomitant therapies are to be obtained). For patients who completed the trial with persisting adverse event(s) at Visit 15/EOT and patients who prematurely discontinued the 52-week treatment, a Visit 15/EOT and a Visit 16 (as the follow up-visit, physical examination, vital signs, and safety lab and FPG measurement should be performed additionally) should be performed after 7 days of the Visit15/EOT (with +7 days allowance) as clinic visits.
- 22. Only blood sampling for haematology and urine dipstick test will be performed.
- 23. Blood sample can be taken at any time in non-fasted state.

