## **6. GENERAL ANALYSIS DEFINITIONS**

### **6.1 TREATMENTS**

For efficacy analyses, data up to 7 days after last treatment intake will be considered as on-treatment for HbA1c and waist circumference, and 1 day for all other efficacy endpoints. For safety analyses, data up to 7 days after last treatment intake will be considered as on-treatment for AEs, 3 days for safety lab measurements and 1 day for pulse rate. For further details see [Table 6.7: 1](#). For this purpose, the following treatment regimens and study intervals will be defined in [Table 6.1: 1](#). More detailed information is provided in the trial Analysis Data Set plan.

Table 6.1: 1 Treatment regimens / study intervals

Label	Interval	Start date	Start time
Screening	Screening period	Date of informed consent	00:00
Run-in*	Placebo Run-in period	Date of first administration of placebo medication	Time of first administration of placebo medication, 12:00 if missing
• Empa10 mg/Placebo for Empa25 mg • Empa25 mg/Placebo for Empa10 mg	Double-blind treatment period	Date of first administration of 52-week double-blind study medication	Time of first administration of 52-week double-blind study medication, 12:00 if missing
Post-treatment	Post-treatment	Date of last intake of study drug + X** +1 day	00:00
Post-study	Post-study	Last contact date +1 day	00:00

\* There is switch period which consists of titration period and washout period between screening period and placebo run-in period. After screening period, patients of inclusion criterion 2-A proceed to placebo run-in period, patients of inclusion criterion 2-B proceed to washout period prior to placebo run-in period, patients of inclusion criterion 2-C proceed to titration period then washout period prior to placebo run-in period.

\*\* The endpoint specific follow-up periods for the assignment to active treatment are presented in detail in [Section 6.7](#).

The efficacy analyses will follow the intention-to-treat (ITT) principle in assigning patients to treatment groups, i.e., patients will be analysed as randomised.

Safety analyses will assign patients to the treatment group as treated. If a patient erroneously receives the wrong trial drug, the patient will be analysed as per the first treatment received.

Additionally, the AEs with an onset during the time of the incorrect study treatment will also be tabulated and listed separately.

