## **6.7 BASELINE, TIME WINDOWS AND CALCULATED VISITS**

With regard to efficacy and safety endpoints, the term “baseline” refers to the last observed measurement prior to administration of any randomised study medication.

Measurements taken prior to the first intake of randomised study medication will be considered pre-treatment values. These pre-treatment values will be assigned to a visit according to the nominal visit number as record on the eCRF or provided by the laboratory.

The date and clock time of the first drug administration will be used to separate pre-treatment from on-treatment values. Measurements taken after the first intake of randomised study drug will be considered on-treatment values if they have been obtained up to end of the parameter specific follow-up period as defined in [Table 6.7: 1](#) below and will be assigned to the randomised study drug for efficacy analyses and to the first study drug taken for safety analyses.

Measurements taken after the end of the endpoint specific follow-up period and after the last intake of study drug will be considered post-treatment values.

**Table 6.7: 1** Endpoint specific follow-up period for the assignment to active treatment

Endpoint	Last day of assignment to treatment phase (days after study drug stop date)
Efficacy	
HbA1c	7
FPG	1
Body weight	1
Blood pressure	1
Insulin and glucagon	1
Waist circumference	7
Safety	
Adverse events	7
Safety laboratory measurements	3
Pulse rate	1

On-treatment efficacy and safety measurements will be assigned to visits based on time windows around the planned visit dates. These time windows are defined based on the planned number of days after the date of first administration of study drug (usually this is at Visit 7).

The midpoint between two on-treatment visits defines the end of a time window, with the midpoint being included in the time window of the preceding visit. The end of the time window of the last on-treatment visit is endpoint dependent (see [Table 6.7: 1](#)).

**Table 6.7: 2** Time windows for on-treatment HbA1c, body weight, and waist circumference measurements scheduled for each on-treatment visit

Visit number	Visit label	Planned days	Time window (actual days on treatment)	
			Start	End A
7	Baseline	0	NA	1 B
9	Week 8	56	2	98
11	Week 20	140	99	196
13	Week 36	252	197	308
15	Week 52/EoT	364	309	Study drug stop date + X days

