A In case of premature discontinuation of the study drug a Visit 15 has to be performed. If such a Visit 15 falls into the time window of a previous visit, measurements will be assigned to this previous visit and the visit value will be determined as described below. In this case the time window for the visit that includes Visit 15 will end X days after the study drug stop date, including Day X. The definition of X is endpoint specific, cf. [Table 6.7: 1](#). As visit 16 is optional, no time window for this visit is planned.

B Only values taken prior to the start of treatment with randomised study drug can be considered baseline values. Time windows will be used for assignment of measurements to scheduled visits.

**Table 6.7: 3** Time windows for on-treatment FPG, vital sign, and safety lab measurements scheduled for each on-treatment visit

Visit number	Visit label	Planned days	Time window (actual days on treatment)	
			Start	End A
7	Baseline	0	NA	1 B
8	Week 4	28	2	42
9	Week 8	56	43	70
10	Week 12	84	71	112
11	Week 20	140	113	168
12	Week 28	196	169	224
13	Week 36	252	225	280
14	Week 44	308	281	336
15	Week 52/EoT	364	337	Study drug stop date + X days

A In case of premature discontinuation of the study drug a Visit 15 has to be performed. If such a Visit 15 falls into the time window of a previous visit, measurements will be assigned to this previous visit and the visit value will be determined as described below. In this case the time window for the visit that includes Visit 15 will end X days after the study drug stop date, including Day X. The definition of X is endpoint specific, cf. [Table 6.7: 1](#). As visit 16 is optional, no time window for this visit is planned.

B Only values taken prior to the start of treatment with randomised study drug can be considered baseline values. Time windows will be used for assignment of measurements to scheduled visits.

**Table 6.7: 4** Time windows for on-treatment biomarkers measurement and bone markers scheduled for each on-treatments visit

Visit number	Visit label	Planned days	Time window (actual days on treatment)	
			Start	End A
7	Baseline	0	NA	1 B
15	Week 52/EoT	364	2	Study drug stop date + X days

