## **7.8.2     Laboratory data**

The analyses of laboratory data will be descriptive in nature and will be based on BI standards (4). Baseline for safety laboratory parameters will be the last available measurement before the start of randomised study drug. Laboratory measurements taken up to 3 days after the last administration of randomised study drug will be considered as on-treatment. For continuous safety laboratory parameters, standardised and normalised values will be derived as well as the differences from baseline. The process of standardisation and normalisation as well as standard analyses for safety laboratory data is described in the BI guideline (4). All analyses considering multiple of times upper limit of normal (ULN) will be based on original and not normalised data.

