### General laboratory evaluation

Descriptive statistics with normalised values will be provided by treatment group for baseline, on-treatment values and for changes from baseline. Laboratory values will be compared to their reference ranges and frequency tables will be provided for the number of patients within and outside the reference range at baseline and the last measurement on treatment. Frequency tables for categorical laboratory values categorised by value at baseline and last value on treatment will be shown. Frequency tables will summarise the number of patients with potentially clinically significant abnormalities. In addition, descriptive statistics with normalised values and frequency for categorical laboratory values will be provided for overtime in the CTR, Appendix 16.1.9.2.

General laboratory evaluation will also be provided for bone markers.

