Descriptive statistics will be created for creatinine and eGFR values over time. Descriptive statistics for eCcr will be presented in the CTR, Appendix 16.1.9.2. These data will be used to create plots of the parameters over time. Subgroups tables of these descriptive statistics at Week 52 will also be presented for age subgroups.

A summary will also be created representing the number of patients with creatinine on treatment  $\geq 2$  x baseline and greater than the upper limit of normal.

A shift table from baseline to last value on treatment for eGFR (Japanese equation) will be provided in the CTR, Section 15 and eCcr (Cockcroft-Gault) will be provided in the CTR, Appendix 16.1.9.2.

In addition, urine albumin and urine albumin / creatinine ratio will be summarised in the CTR. Urine creatinine does not have a reference range and it is determined to calculate the albumin / creatinine ratio. Only the albumin / creatinine ratio will be analysed as for urine creatinine, no normalised values can be derived. In cases where urine albumin values are reported to be below the quantification limits (e.g. <3 mg/L), the albumin / creatinine ratio is determined as missing and will not be replaced by estimated values.

Four summaries will be presented for the descriptive statistics of urine albumin/creatinine ratio by baseline value (normal ( $<30$ mg/g), microalbuminuria ( $30-300$  mg/g) and macroalbuminuria ( $\geq 300$  mg/g)), descriptive statistics of urine albumin by baseline value ( $<20$ mg/L,  $20-200$ mg/L and  $\geq 200$ mg/L) and frequency of transitions from baseline based on the before mentioned categories.

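### Safety labs taken at an early end-of-treatment visit on days 4 to 7 after the last dose are allowed by the protocol but drop out of the on-treatment laboratory tables

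*SAP*

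**What the plan says.** Footnote 20 of the protocol flow chart covers early discontinuation from double-blind treatment: "Visit 15/EOT visit has to be performed within 7 days of the last dose of the study drugs". The flow chart schedules the full safety laboratory panel at that visit.

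SAP 6.1 sets different on-treatment limits by type of data: "data up to 7 days after last treatment intake will be considered as on-treatment for AEs, 3 days for safety lab measurements". Table 6.7: 1 repeats the 3-day limit for safety laboratory data, and SAP 7.8.2 states it again: "Laboratory measurements taken up to 3 days after the last administration of randomised study drug will be considered as on-treatment". SAP 6.7 settles the status of later values: "Measurements taken after the end of the endpoint specific follow-up period and after the last intake of study drug will be considered post-treatment values". The footnotes to the visit-window tables apply this to an early EOT visit: "In this case the time window for the visit that includes Visit 15 will end X days after the study drug stop date". For safety labs X is 3.

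Several laboratory outputs depend on that status. The general evaluation compares patients "within and outside the reference range at baseline and the last measurement on treatment" and shows categorical values in the same way. For renal function the SAP plans an eGFR shift table to the last on-treatment value, and a doubling count: "A summary will also be created representing the number of patients with creatinine on treatment" at least twice baseline and above the upper limit of normal.

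**The concern.** The visit allowance (7 days) and the laboratory limit (3 days) do not match. A sample taken exactly as the protocol permits can be unusable for the tables it was meant to feed.

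The loss is tied to outcome. Completers should take their last dose about a day before Visit 15, so their samples count. Only patients who stop early can lose the EOT sample, and some of them stop because of adverse events. These are the patients whose laboratory values at stopping matter most in a trial with a safety objective.

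The report can also disagree with itself. Creatinine doubling above the upper limit of normal is a protocol-defined adverse event of special interest, and adverse events count to day 7. If doubling is found at an EOT visit on day 5, the patient can appear in the special-interest table and be absent from the laboratory summary of the same threshold.

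**Working it through.** **Inputs**

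- Planned size 64 (32 per arm), at least 50 completers, about 20% dropout: protocol 7.7.
- Early EOT visit permitted to day 7: flow chart footnote 20.
- Laboratory limit day 3: SAP 6.1, Table 6.7: 1 and 7.8.2.
- Full chemistry during treatment at Weeks 4, 8, 20, 36 and 52. Weeks 12, 28 and 44 have haematology and urine dipstick only: flow chart and footnote 22.
- Dose 22 to 26 hours before the visit dose: protocol 4.1.4.
- Lag from last dose to an early EOT visit: not given beyond the 7-day ceiling, so it is assumed and varied below.

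**The plan's own figure.** 50 / (1 − 0.20) = 62.5, rounded up to 63, then to 64 for two equal arms. This reproduces the stated 64. Expected completers are 0.80 × 64 = 51.2, and expected early stoppers are 0.20 × 64 = 12.8, about 13.

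**Which lag days are lost.** Days 4, 5, 6 and 7 are allowed for the visit but lie outside the laboratory limit.

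**Expected number affected** (12.8 × share of EOT visits falling on days 4 to 7). In the clustered rows the probability of day k is proportional to r^k for k = 0 to 7, so the share is (r^4 + … + r^7) / (r^0 + … + r^7) = r^4 / (1 + r^4).

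| Assumed lag | Share lost | Patients |
|---|---|---|
| All within 3 days | 0 | 0 |
| Clustered early, r = 0.5 | 0.0625 / 1.0625 = 6% | 0.8 |
| Clustered early, r = 0.7 | 0.2401 / 1.2401 = 19% | 2.5 |
| Clustered early, r = 0.8 | 0.4096 / 1.4096 = 29% | 3.7 |
| Clustered early, r = 0.9 | 0.6561 / 1.6561 = 40% | 5.1 |
| Uniform, days 0 to 7 | 4/8 = 50% | 6.4 |
| Uniform, days 1 to 7 | 4/7 = 57% | 7.3 |
| All on days 4 to 7 | 100% | 12.8 |

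One patient is 1/32 = 3.1% of an arm.

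**Age of the value that replaces it.** Gaps between full chemistry panels are 8 − 4 = 4, 20 − 8 = 12, 36 − 20 = 16 and 52 − 36 = 16 weeks. Unless an unscheduled sample exists, the last on-treatment chemistry comes from Week 4, 8, 20 or 36 and is nominally up to 16 weeks older. Haematology is drawn at every scheduled clinic visit on treatment, so its gap is at most 8 weeks.

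**Can Visit 16 fill the gap?** No. It takes place 7 days after Visit 15, and the SAP gives it no time window.

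**The case against.** The 3-day limit is a deliberate, endpoint-specific choice, stated the same way in three places in the SAP. Protocol 3.2 says the pharmacodynamic effect lasts about 3 days after the last dose. The SAP does not cite this, but it is a plausible basis. This stands: the limit is not an internal contradiction and is reasonable for the main tables. It does not show that an abnormality arising on drug has resolved by day 3, and the same SAP allows 7 days for adverse events.

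Important findings have other routes. Under protocol 5.3.7, laboratory changes judged clinically relevant are recorded as adverse events, and these count to day 7. Renal and hepatic events of special interest are tabulated from case report form flags, and hepatic events are adjudicated. So a reader who inferred that discontinuation labs vanish from the safety tables would go too far. What remains is that the adverse event route depends largely on the investigator's judgement or flag, whereas shift and threshold tables do not.

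A reader might also infer that these labs are often lost. The documents do not support that. They give a ceiling and no distribution, and some features favour prompt visits or retained values. If a new antidiabetic regimen is started, Visit 15 must come first (protocol 3.3.4.1). A missing stop date is set to the EOT visit date (SAP 6.6), which keeps the sample. In the other direction, nothing requires a visit by day 3, and the SAP's violation code C3.03 flags only gaps above 7 days.

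Finally, a reader might conclude that the tables will look too favourable. That is possible if the older value is more normal. But a sample on days 5 to 7 may already have recovered, and putting it in place of an on-drug value could hide an abnormality.

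**Conclusion.** The point holds for a defined set of outputs: the reference-range and categorical tables of last value on treatment, the eGFR shift table and the creatinine-doubling summary. EOT labs on days 4 to 7 after early stopping are compliant with the protocol and do not enter them. It is not established for the clinically-significant-abnormality and liver-enzyme summaries. The SAP text does not restrict these to on-treatment values, and it refers to a sponsor guideline that is not part of the documents; their window needs to be stated.

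The number affected lies between 0 and about 13. About 6 to 7 follows only from uniform lags, and about 1 to 5 from lags clustered early. All these figures assume that 20% stop early and that each of them has an EOT sample. Since EOT procedures after stopping depend on the patient's agreement, fewer may attend. Completers are unaffected if dosing follows the plan. The direction of bias is uncertain. The primary endpoint, drug-related adverse events, is unaffected, and all safety analysis is descriptive. This is a cheap improvement to the plan rather than a flaw in its main result.

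**What to change.** Before database lock, amend SAP 6.7 and 7.8.2 as follows.

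1. Keep the 3-day tables as the main laboratory analysis.
2. Add a supplementary run of the reference-range and categorical tables, the eGFR shift table and the creatinine-doubling summary, with X = 7 days for Visit 15/EOT labs. This matches the adverse event period and admits every EOT sample the protocol allows.
3. State that the clinically-significant-abnormality and liver-enzyme summaries include EOT labs to day 7.
4. Report, by treatment group, how many discontinuers had EOT labs after day 3. This replaces the assumed lags above with the actual number.

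The cost is a second run of existing programs and a few added pages. The downside is small: some added values are partly off drug, and the 3-day tables remain beside them for comparison. No visit timing or data collection changes.

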### General laboratory evaluation

Descriptive statistics with normalised values will be provided by treatment group for baseline, on-treatment values and for changes from baseline. Laboratory values will be compared to their reference ranges and frequency tables will be provided for the number of patients within and outside the reference range at baseline and the last measurement on treatment. Frequency tables for categorical laboratory values categorised by value at baseline and last value on treatment will be shown. Frequency tables will summarise the number of patients with potentially clinically significant abnormalities. In addition, descriptive statistics with normalised values and frequency for categorical laboratory values will be provided for overtime in the CTR, Appendix 16.1.9.2.

General laboratory evaluation will also be provided for bone markers.

### Hepatic laboratory parameters

To support analyses of liver related adverse drug effects, patients with following alterations of hepatic laboratory parameters at randomisation at Visit 7 are of special interest:

- An elevation of AST and/or ALT  $\geq 3$ xULN combined with concomitant or subsequent total bilirubin  $\geq 2$ xULN in a 30 day period after AST/ALT elevation and/or
- Marked peak aminotransferase (ALT, and/or AST) elevations  $\geq 5$ xULN

The start of the 30 day time span is triggered by each liver enzyme elevation above the defined thresholds. Patients who fulfil one or two of the criteria for ALT/AST or total bilirubin(TBILI) but have no information available for the remaining parameter(s) at the same time-point or within the 30 day time window will not be listed under “ALT and/or AST  $\geq 3$ xULN with TBILI  $\geq 2$ xULN” or “ALT and/or AST  $\geq 5$ xULN”.

Summaries will be presented for patients with elevated liver enzymes. Details on patients with elevated liver enzymes will also be listed.

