3.3.3 Exclusion criteria

- 1. Uncontrolled hyperglycaemia with a glucose values >270 mg/dL (>15.0 mmol/L) after an overnight fast during switch/washout/placebo run-in period and confirmed by a second measurement (not on the same day and one of the measurement should be performed at the investigational site after overnight fast)
- 2. Patients who are drug-naïve at Visit 1 (screening visit) or treat with any of insulin, thiazolidine dione, SGLT-2 inhibitor within 10 weeks prior to informed consent.
- 3. Acute coronary syndrome (ST elevation myocardial infarction [STEMI], non-STEMI, and unstable angina pectoris), stroke or transient ischemic attack (TIA) within 12 weeks prior to informed consent
- 4. Indication of liver disease, defined by serum levels of either alanine aminotransferase (ALT [SGPT]), aspartate aminotransferase (AST [SGOT]), or alkaline phosphatase (ALP) above 3 x upper limit of normal (ULN) as determined during screening and/or switch/washout/placebo run-in period
- 5. Impaired renal function, defined as eGFR <45 mL/min/1.73m² (Japanese equation) as determined during screening and/or switch/washout/placebo run-in period

- 6. Any previous (within 2 years prior to informed consent) bariatric surgery or other gastrointestinal surgery that induce chronic malabsorption
- 7. Medical history of cancer (except for basal cell carcinoma) and/or treatment for cancer within the last 5 years of informed consent
- 8. Blood dyscrasias or any disorders causing haemolysis or unstable red blood cells (RBC) (e.g., malaria, babesiosis, haemolytic anaemia)
- 9. Contraindications to liraglutide and empagliflozin according to the Japanese label
- 10. Known allergy or hypersensitivity to liraglutide or empagliflozin
- 11. The patients who are not able to receive liraglutide 0.9 mg/day for 10 weeks prior to placebo run-in period and who do not treat with the same dose during run-in period
- 12. Treatment with anti-obesity drugs (e.g. mazindol) within 12 weeks prior to informed consent or any other treatment at the time of screening and/or switch/washout/placebo run-in period (i.e. surgery, aggressive diet regimen, etc.) leading to unstable body weight
- 13. Current treatment with systemic steroids(exclude inhaled or local steroids) at time of informed consent or change in dosage of thyroid hormones within 6 weeks prior to informed consent or any other uncontrolled endocrine disorder except T2DM

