The term AESI relates to any specific AE that has been identified at the project level as being of particular concern for prospective safety monitoring and safety assessment within this trial, e.g. the potential for AEs based on knowledge from other compounds in the same class. AESI need to be reported to the Sponsor's Pharmacovigilance Department within the same timeframe that applies to SAE, see Section 5.3.7.

Page 48 of 73

Proprietary confidential information © 2017 Boehringer Ingelheim International GmbH or one or more of its affiliated companies

The following are considered as AESIs:

Metabolic acidosis, ketoacidosis and diabetic ketoacidosis (DKA)

In case of metabolic acidosis, ketoacidosis and DKA further investigations should be done according to the medical judgement and the clinical course until a diagnosis is made and/or the patient is recovered.

DKA is defined as a state in which a severe shortage of insulin and an increase in counter regulatory hormones combine to induce hyperglycemia (≥250 mg/dL), hyperketonemia (increased β-hydroxybutyric acid), and acidosis (pH<7.30; bicarbonate concentration <18 mEq/L), and as defined by the Japanese guideline, Evidence-based Practice Guideline for the Treatment for Diabetes in Japan 2013 [R13-3738].

Investigators should note that not all criteria in the described above need to apply for the diagnosis of DKA, and clinical judgement should also be taken into consideration. Due to its mechanism of action, empagliflozin may potentially modify the clinical presentation of DKA which may occur at lower plasma glucose levels than stated above.

Hepatic injury

A hepatic injury is defined by the following alterations of hepatic laboratory parameters at randomisation at Visit 7:

- An elevation of AST and/or ALT ≥3 fold ULN combined with an elevation of total bilirubin ≥2 fold ULN measured in the same blood draw sample, and/or
- Marked peak aminotransferase (ALT, and/or AST) elevations ≥5 fold ULN

These lab findings constitute a hepatic injury alert and the patients showing these lab abnormalities need to be followed up according to the "DILI checklist" provided via the RDC system.

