In case of clinical symptoms of hepatic injury (icterus, unexplained encephalopathy, unexplained coagulopathy, right upper quadrant abdominal pain, etc.) without lab results (ALT, AST, total bilirubin) available, the investigator should make sure these parameters are analysed, if necessary, in an unscheduled blood test. Should the results meet the criteria of hepatic injury alert, the procedures described in the DILI checklist should be followed.

Decreased renal function

A decreased renal function is defined by the following alterations of renal laboratory parameters:

• Creatinine value shows a ≥2 fold increase from baseline and is above the upper limit of normal (ULN)

The patient with any of the events is mentioned above need to be followed up appropriately. The investigator should consider which, if any, concomitant therapies should not be taken during evaluation. Discontinued treatments can be reintroduced per investigator discretion.

For any of these AESI, the investigator should report the event to the local pharmacovigilance centre immediately (within 24 hours of being informed, and without

Boehringer Ingelheim BI Trial No.:1245.106 c03122586-03

Trial Protocol

20 JAN 2017 Page 49 of 73

Proprietary confidential information © 2017 Boehringer Ingelheim International GmbH or one or more of its affiliated companies

waiting for confirmation of the result via a second measurement) on the SAE form, even if they do not meet any of the seriousness criteria.

The investigator should collect the relevant unscheduled laboratory sample(s) as soon as possible (i.e. lipase, creatinine, or hepatic enzymes). Further follow-up laboratory tests should be done according to medical judgement depending on the clinical course.

Events involving lower limb amputation

This definition includes amputation (i.e. resection of a limb through a bone), disarticulation (i.e. resection of a limb through a joint) and auto-amputations (i.e. spontaneous separation of non-viable portion of the lower limb).

Not included in this definition are debridement (removal of callus or dead tissue), procedures on a stump (like stump revision, drainage of an abscess, wound revision etc.) and other procedures (e.g., nail resection or removal) without a concomitant resection of a limb (amputation or disarticulation).

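### The hepatic criteria are tied to the pre-dose Visit 7 draw (SAP 7.8.2, Protocol 5.3.6.1), and the SAP's missing-parameter sentence can drop patients who meet them; both need rewording

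*SAP*

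**What the plan says.** **Timing.** Under Hepatic laboratory parameters, SAP 7.8.2 states that "patients with following alterations of hepatic laboratory parameters at randomisation at Visit 7 are of special interest". Protocol 5.3.6.1 uses the same anchor for the hepatic adverse event of special interest (AESI): "A hepatic injury is defined by the following alterations of hepatic laboratory parameters at randomisation at Visit 7".

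**Criteria.** Both documents give two. The first combines AST and/or ALT ≥3×ULN with total bilirubin ≥2×ULN. The second is ALT and/or AST ≥5×ULN, with no bilirubin component. For the combined criterion the protocol wants bilirubin "measured in the same blood draw sample". The SAP accepts bilirubin at the same time or within 30 days after the enzyme rise.

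**Missing values.** The SAP adds a rule for incomplete data: "Patients who fulfil one or two of the criteria for ALT/AST or total bilirubin(TBILI) but have no information available for the remaining parameter(s". If the missing information is not available at the same time-point or within the 30 days, these patients are not to appear under the combined heading or under the ≥5×ULN heading. The SAP names both headings.

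**Other hepatic output.** The same SAP section provides summaries of elevated liver enzymes and adds that "Details on patients with elevated liver enzymes will also be listed".

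**The concern.** The category exists to help detect drug effects on the liver, so its enzyme trigger has to come from values obtained after randomised treatment has started. A trigger fixed to the randomisation visit can only pick up baseline findings.

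The missing-value rule raises a second problem. Both criteria accept either aminotransferase, and the ≥5×ULN criterion does not use bilirubin at all. A rule that withholds a heading because an unneeded value is absent removes patients who have already met that criterion.

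At stake is the accuracy of one hepatic listing, and possibly of the AESI category, in a trial of 64 randomised patients whose main purpose is safety. In a trial of that size each qualifying liver case counts.

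**Working it through.** No planned figure is involved, so the check sets the passages side by side and applies the rules as written to test patients.

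**1. Is the Visit 7 draw pre-dose?** Yes. Protocol 5.3.3 requires safety samples before drug intake. Protocol 6.2.2 puts randomisation and dispensing last in the visit, with the day's dose given after all procedures. SAP 6.7 classes anything measured before the first randomised dose as pre-treatment.

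**2. What does the literal anchor leave out?** The flow chart schedules safety laboratory tests after Visit 7 at Visits 8 to 15. Footnote 22 limits Visits 10, 12 and 14 to haematology and dipstick. That leaves five on-treatment chemistry draws (Visits 8, 9, 11, 13 and 15). Read literally, none of the five can supply the enzyme trigger.

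**3. Is the literal reading intended?** The documents indicate that it is not.
- The SAP says "The start of the 30 day time span is triggered by each liver enzyme elevation above the defined thresholds", which presupposes elevations at more than one time.
- Protocol 5.3.6.1 applies the alert to unscheduled tests in patients with symptoms: "Should the results meet the criteria of hepatic injury alert, the procedures described in the DILI checklist should be followed".
- Exclusion criterion 4 (Protocol 3.3.3) removes patients with ALT, AST or ALP "above 3 x upper limit of normal (ULN) as determined during screening and/or switch/washout/placebo run-in period". A category restricted to Visit 7 would hold almost only patients whose rise first appears on that day.
- The neighbouring renal summary in SAP 7.8.2 is explicitly for creatinine on treatment.

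**4. Missing-value rule and anchor applied to test patients** (values in ×ULN; illustrative, not trial data):

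| Draw | ALT | AST | Bilirubin | Criterion met | Missing-value rule as written | Visit 7 anchor as written | After the fix |
|---|---|---|---|---|---|---|---|
| On treatment | 6 | 1 | 0.8 | ≥5 | listed | not listed | listed |
| On treatment | 6 | 1 | missing | ≥5 | not listed | not listed | listed |
| On treatment | 6 | missing | 0.8 | ≥5 | not listed | not listed | listed |
| On treatment | 4 | missing | 2.5, same draw | combined | not listed | not listed | listed |
| On treatment | 4 | 4 | missing | cannot be judged | not listed | not listed | not listed |
| Visit 7, pre-dose | 6 | 1 | 1 | ≥5, at baseline | listed | listed | not listed (baseline) |

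Rows 2 to 4 are the defect in the missing-value rule: the criterion is met on the available data and the sentence still withholds the heading. Row 5 is where the sentence is right, because bilirubin is needed and absent.

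**5. Protocol against SAP on bilirubin.** A same-draw bilirubin always satisfies the SAP's 30-day span, so on bilirubin timing alone the SAP is the wider definition. Row 4 shows that this does not make the SAP set contain the protocol set: that patient meets the protocol's same-draw rule and is kept off the SAP's combined heading.

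**The case against.** **The intent is clear.** The post-dose intent can be read from the text around the Visit 7 phrase, and a programmer would probably follow it. That stands, and it is why this is treated as a slip. A reader might infer that the sponsor means to assess the liver at baseline only, or that on-treatment rises would go unreported. The documents support neither. They do still contain the phrase, in both places.

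**The missing-value sentence has a harmless reading.** Each heading may be withheld only where a parameter it needs is absent; for example, high bilirubin with no aminotransferase value cannot be placed under ≥5×ULN. That reading fits the criteria. The sentence does not say so, however, and it names the ≥5×ULN heading outright.

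**The practical effect is small.** This stands. ALT, AST and bilirubin belong to one chemistry panel (Protocol 5.3.3), so a lone missing value should be uncommon. An affected patient could still appear in the elevated-enzyme listing, the table of clinically significant abnormalities (SAP 7.8.2), the AESI table from eCRF flags and the hepatic SMQ tables (SAP 7.8.1.5), or the adjudicated events (SAP 7.8.1.9, Protocol 3.1.1.1).

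**The laboratory period is already defined.** This also stands. SAP 6.1, Table 6.7: 1 and 7.8.2 give three days after the last dose, and SAP 6.7 classes later values as post-treatment. No new period or extra post-treatment listing is needed.

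**The operative rule may lie elsewhere.** The SAP refers to a sponsor laboratory guideline and an analysis data set plan, and the protocol to a hepatic charter. These were not available. Whatever they contain, the wording in the two current documents remains incorrect.

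**Conclusion.** Wrong as written, and minor. Followed literally, the Visit 7 anchor admits no on-treatment enzyme elevation to the hepatic category, and the missing-value sentence withholds a heading from patients whose available values already meet the criterion. The difference between same-draw and 30-day bilirubin is a matter for reconciliation or labelling.

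The effect is confined to this listing and possibly the AESI category. The AESI part depends on how investigators set the eCRF flag; one who follows the protocol's instruction on unscheduled tests would not apply a Visit 7 limit. The primary endpoint is unaffected. A reader might infer that liver cases would disappear from the report. The documents do not show that: they give no rate of missing values, several other outputs remain, and no number of lost patients is claimed here.

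The conclusion rests on reading the missing-value sentence by its plain wording, and on no unseen document overriding it.

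**What to change.** In SAP 7.8.2, Hepatic laboratory parameters:

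- **(a) Timing.** Replace the Visit 7 phrase with on-treatment values after the first dose of randomised drug, using the laboratory on-treatment period already set in SAP 6.7 and 7.8.2. Leave the 30-day bilirubin span as it is.
- **(b) Missing values.** Reword the sentence so that one available ALT or AST value is enough for either heading. Only a missing bilirubin, at the same time-point and throughout the 30 days, should keep a patient off the combined heading. Every patient with an on-treatment ALT or AST ≥5×ULN is then listed.
- **(c) Consistency.** The sponsor should reconcile Protocol 5.3.6.1 and SAP 7.8.2 on timing and on same-draw versus 30-day bilirubin, or label the two tables as using different definitions.

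Items (a) and (b) are a few words in the SAP, with no new data or procedures. Changing the protocol sentence needs an amendment with IRB approval (Protocol 8.1). It can wait for the next amendment, with the tables labelled in the report meanwhile.
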